ICH	International Council for Harmonization of Technical Requirements for Registration of Pharmaceuticals for Human Use	
IEC	Independent Ethics Committee	
IGA	Investigator's Global Assessment	
IL	Interleukin	
IN	Investigator Notification	
INR	International Normalized Ratio	
IRB	Institutional Review Board	
IRT	Interactive Response Technology	
IUD	Intrauterine device	
i.v.	intravenous	
LDH	Lactate Dehydrogenase	
LFT	Liver function test	
MCPMod	Multiple Comparison Procedures – Modelling	
MDRD	Modification of Diet in Renal Disease	
MedDRA	Medical Dictionary for Regulatory Activities	
mg	milligram(s)	
MI	Multiple imputation	
mL	milliliter(s)	
MMRM	Mixed effect Model Repeat Measurement	
NOAEL	No observed adverse effect level	
NRS	Numerical rating scale	
o.d.	once daily	
PCR	Protein creatinine ratio	
PD	Pharmacodynamic(s)	
PoC	Proof of Concept	
PRO	Patient Reported Outcome	
PSW	Premature Subject Withdrawal	
PT	Prothrombin time	
QTc(F)	Corrected QT interval (by Frediricia's formula)	
RNA	Ribonucleic acid	
SAE	Serious Adverse Event	

sCR	serum Creatinine
SUSAR	Suspected Unexpected Serious Adverse Reactions
TBL	Total Bilirubin
TCS	Topical Corticosteroids
TD	Treatment discontinuation
TdP	Torsades de Pointes
Th2	T-helper 2 cells
TSLP	Thymic stromal lymphopoietin
ULN	upper limit of normal
WBC	white blood cell(s)
WHO	World Health Organization
WoC	Withdrawal of consent
WOCBP	Women of child bearing potential

Novartis Amended Protocol Version 03 (clean)	Confidential	Page 10 Protocol No. CZPL389A2203

Baseline	Day 1: subjects who are eligible will be randomized
Control drug	Drugs(s) used as a comparator to reduce assessment bias, preserve blinding of investigational drug, assess internal study validity, and/or evaluate comparative effects of the investigational drug
Dosage	Dose of the study treatment given to the subject in a time unit (e.g. 30 mg once daily)
Electronic Data Capture (EDC)	Electronic data capture (EDC) is the electronic acquisition of clinical study data using data collection systems, such as Web-based applications, interactive voice response systems and clinical laboratory interfaces.
	EDC includes the use of Electronic Case Report Forms (eCRFs) which are used to capture data transcribed from paper source forms used at the point of care.
Enrollment	Point/time of subject entry into the study at which informed consent must be obtained (e.g. prior to starting any of the procedures described in the protocol)
Investigational drug	The drug whose properties are being tested in the study; this definition is consistent with US CFR 21 Section 312.3 and is synonymous with "investigational new drug" or "investigational medicinal product."
IGA Response	IGA response is defined as achieving an IGA score of 0 (clear) or 1 (almost clear) and at least 2 points reduction from Baseline and no use of confounding therapy as adjudicated up to the assessment time point.
Medication pack number	A unique identifier on the label of each investigational drug package
Patient	A person with the condition of interest being studied
Period	Interval of time in the planned conduct of a study. A period is associated with a purpose (e.g. screening, treatment, follow-up), which applies across all arms of a study.
Personal data	Subject information collected by the Investigator that is transferred to Novartis for the purpose of the clinical trial. This data includes subject identifier information, study information and biological samples.
Subject	A patient participating in this study
Subject number	A unique number assigned to each subject upon signing the informed consent
Randomization number	A unique identifier assigned to each randomized subject, corresponding to a specific treatment arm assignment
Source Data/Document	Source data refers to the initial record, document, or primary location from where data comes. The data source can be a database, a dataset, a spreadsheet or even hard-coded data, such as paper or eSource.
Study drug/ treatment	Any single drug or combination of drugs administered to the subject as part of the required study procedures; includes investigational drug (s), placebo/comparator active drug run-ins or background therapy
Study Treatment Discontinuation (TD)	When the subject permanently stops taking study treatment prior to the defined study treatment completion date
Variable	A measured value or assessed response that is determined in specific assessments and used in data analysis to evaluate the drug being tested in the study

Glossary of terms

Withdrawal of study	Withdrawal of consent from the study occurs only when a subject does not
consent (WoC)	want to participate in the study any longer, and does not allow any further
	collection of personal data

Amendment 3 (02 September 2019)

Amendment rationale

Per the original protocol, even though chronic toxicity studies showed no hepatotoxic effects, due to the fact there was at the time limited human data with ZPL389, subjects were not allowed to have any value of AST/ALT/ALP above the upper limit of normal in order to join this phase 2 study. With the recent results from phase 1 study in healthy volunteers (CZPL389A2101) that tested high exposures of ZPL389, no liver abnormalities were seen. Therefore, exclusion limit for AST/ALT/ALP have been increased to 1.5 ULN to allow patients with only minor elevations of AST/ALT/ALP into the study and to prevent unnecessary exclusion of subjects from the study participation. Subjects would still need to fulfill other criteria (e.g. absence of HBV, HCV, prior liver disease, hepatotoxic concomitant medication) in order to be eligible for the study, and will be closely monitored for LFT during the study, therefore safety of subjects would not be compromised.

A clarification about the use of H1 antihistamines has been added. Unless these have a potential for QT interval prolongation (prohibited for all subjects) or have a sedative effect

used short term (e.g. to treat allergies).

Changes to the protocol

The sponsor has also used this opportunity to make operationally relevant or typographical modifications and/ or provide clarifications.

All changes made to the protocol are listed in the table below.

Section	Changes made		
Section 3.5, Section 5.4 and Section 9.7	Addition of a potential interim analysis		
Section 3.6	Updated with results of pivotal Embryo-fetal development toxicology studies and CZPL389A2101 study		
Section 4	Number of study sites has been updated		
Section 4.2	Clarification added to Exclusion criterion #2 on skin infection Exclusion criterion #10 has been modified to		
	 include subjects with AST/ALT/ALP up to 1.5 upper limit of normal (ULN) 		
	clarify abnormal values for Potassium and Magnesium		
	Allow one central lab retest for lab abnormalities outside the respective cut-off criteria during screening period		
	Clarification added to Exclusion criterion #11 on basal cell carcinoma of the skin		
	Clarification added on the form of hormonal contraception allowed in Exclusion criterion #15		
Section 5.2.2 and Table 5-1	Removal of Vitamin E as prohibited component of moisturizers		
Section 5.5.4	Clarification on the number of doses to be taken until week 16 visit		

, these are allowed if on a stable dose or

Section 5.5.6	Clarification added for use of an alternative TCS as rescue medication
Section 5.5.8, Table 5-1	For subjects who discontinued early, action taken on prohibited medication during follow up period has been modified
	Clarification on the use of H1 Antihistamines
	Information on use of ibuprofen or topical NSAID has been added
Section 6.2	Clarification added for collection of subject's baseline characteristics
Section 6.2.1	Clarification on the type of test done for Hep C
Section 6.5.5.1 and Table 14-2	PT/INR has been added to unscheduled visit
Section 6.5.6.1	Microscopy result entry in CRF has been removed as the result will be available in central laboratory data
Section 6.6.4	Clarification on the requirement of availability of CYP2D6 test results before randomization for subjects taking moderate CYP1A2 inhibitor and adherence to wash out period
Section 7.3	In case of a Liver event, requirement of completion of applicable questionnaire for adjudication has been added
Section 7.5	Any increase from Baseline of 30 msec in QTcF (Fridericia) interval for males and females has been added to the definition of a notable QTc value

Changes to specific sections of the protocol are shown in the track changes version of the protocol using strike through red font for deletions and red underlined for insertions.

IRBs/IECs

A copy of this amended protocol will be sent to the Institutional Review Board (IRBs)/Independent Ethics Committee (IECs) and Health Authorities.

The changes described in this amended protocol require IRB/IEC and Health Authority approval according to local regulations prior to implementation.

The changes herein affect the Informed Consent. Sites are required to update and submit for approval a revised Informed Consent that takes into account the changes described in this protocol amendment.

Amendment 2 (11 September 2018)

Amendment rationale

The protocol is amended to incorporate changes following interim results from Phase I trial in healthy volunteers (CZPL389A2101).

Based on the Phase I study results and potential drug-drug interaction risk, the protocol is amended to include a precautionary measure to minimize the risk of higher exposure to ZPL389 that may occur in subjects who are poor CYP2D6 metabolizers. This measure includes identifying subjects that are poor CYP2D6 metabolizers prior to study treatment start and prohibiting use of moderate inhibitors of CYP1A2 (including hormonal contraception), in these subjects (CYP2D6 metabolizers). As per previous protocol, strong CYP1A2 inhibitors are still prohibited for all subjects. Additionally Phase I study results have shown that more time is needed to achieve than shown by previous studies, therefore the timing of the post dose ECG is changed from 0.5h to 2h. On days of site visits, subjects are asked to fast 3 hours before the visit, ECG parameters may be impacted by the intake of food. However, due to no food effect seen on overall drug exposure in Phase I study, fasting before and after drug intake on non-visit days is no longer necessary.

Changes to the protocol

All changes made to the protocol are listed in the table below.

Section	Changes made
Section 3.1, Figure 3-1 and Table 6-1	The screening period has been extended up to 4 weeks (to allow time to get the), extending the total study duration from 23 to 24 weeks
Section 3.4, Section 4.1, Section 5.2.2 and Section 6	The use of bland emollient has been changed to once daily instead of twice
Section 3.3 and Section 3.6	Updated with relevant interim data from study CZPL389A2101
Section 3.4	Removal of the sentence referring to the extension study as this was misplaced

Section 4.2	Exclusion criteria #15 has been modified to prohibit hormonal contraception for poor CYP2D6 metabolizers (as hormonal contraception is moderate inhibitor of CYP1A2)		
	Deletion of the text about additional exclusion applied by investigator		
Section 4.3 and Section 4.4			
Section 5.4	Clarification on when unblinding would occur		
Section 5.5.4 and Section 6	Fasting requirement before and after taking study medication at home has been removed.		
Section 5.5.6	Allowing hydrocortisone 2.5% ointment as rescue medication for sensitive areas		
Section 5.5.8	Addition of moderate CYP1A2 inhibitors as prohibited concomitant medication for CYP2D6 poor metabolizers		
	Clarification that eye drops are not considered systemic immunosuppressive treatment.		
Section 5.6	Clarification on EOT, Withdrawal of consent and early study termination		
Section 6	Clarification that subjects should be fasted 3 hours before site visits and until the last ECG is performed		
	Visit days for Week 16 and Week 20 visits have been updated to 113 and 141 days respectively. Therefore dosing at site on Week 16 visit has been removed. A clarification has been added on when sample will be collected at Week 16 visit		
	Unplanned ECG has been added in the table of assessment and time of Post dose ECG at Baseline and Week 4 changed from 0.5h to 2 hours postdose		
Section 6.6.1 and Section 8.3	Allowing Patient Reported Outcomes (PROs) to be collected on paper should the electronic device not be working		

Changes to specific sections of the protocol are shown in the track changes version of the protocol using strike through red font for deletions and red underlined for insertions.

IRBs/IECs

A copy of this amended protocol will be sent to the Institutional Review Board (IRBs)/Independent Ethics Committee (IECs) and Health Authorities.

The changes described in this amended protocol require IRB/IEC and Health Authority approval according to local regulations prior to implementation.

The changes herein affect the Informed Consent. Sites are required to update and submit for approval a revised Informed Consent that takes into account the changes described in this protocol amendment

Amendment 1 (30 January 2018)

Rationale

The original protocol is amended to incorporate health authority feedback prior to the start of enrolment as listed in the table below.

Section	Changes made	
Section 4.1	EASI score at Screening visit for inclusion into trial changed from 12 to 16	
Section 4.2 and Section 7.5	Exclusion threshold and notable value for resting QTcF for female changed from ≥460 to ≥470 msec	
Section 5.6 and Section 7.5	Discontinuation criteria for cardiac disorders aligned with CTCAE grade 2 events	
Section 6	Time of Post dose ECG at Baseline and Week 4 changed to 30 mins postdose	

The sponsor has used this opportunity to simplify and update sections regarding sample size and statistical analysis. Other minor corrections were made such as adding the requirement for fasting 1 hour before ECG measurements.

All changes from the original protocol v00 are indicated in red underlined text (insertions) or red strikethrough (deleted text) in the track changes version of this protocol amendment.

A copy of this amended protocol will be sent to the Institutional Review Board (IRBs)/Independent Ethics Committee (IECs) and Health Authorities.

The changes herein affect the Informed Consent. Sites are required to update and submit for approval a revised Informed Consent that takes into account the changes described in this protocol amendment.

Protocol summary

ind, placebo-controlled multicenter dose ranging study to efficacy of multiple oral ZPL389 doses in patients with c dermatitis (ZEST Trial) ety and efficacy of ZPL389 doses in patients with moderate s
ety and efficacy of ZPL389 doses in patients with moderate is
is to determine the dose-response relationship of ZPL389
is to determine the dose-response relationship of ZPL389
is to determine the dose-response relationship of ZPL389
is to determine the dose-response relationship of ZPL389
parameters in order to define the most appropriate dose(s) of ZPL389 in subjects with moderate to severe atopic
response relationship of ZPL389 in subjects with moderate is assessed by Investigator's global assessment response
dose-response relationship of ZPL389 in subjects with pic dermatitis assessed using the percent change from and Severity Index after 16 weeks of treatment
y across different dose levels as assessed by Eczema Area nvestigator's global assessment compared to placebo over
nd tolerability of different doses of ZPL389 as compared to
double-blind, placebo-controlled, parallel-group study to cy of ZPL389 in subjects with moderate to severe atopic dy duration up to 24 weeks
consist of female and male subjects aged 18 years or evere atopic dermatitis
sent Ititis (according to American Academy of Dermatology that has been present for at least 1 year before Baseline. Itopic dermatitis defined as: Ind Severity Index ≥16 at Screening and at Baseline Iobal assessment 3 or 4 on a 5-point scale (at screening

	treatments are otherwise medically inadvisable (e.g., because of important side effects or safety risks)		
	Candidate for systemic treatment		
	 Any skin disease that, in the opinion of the investigator, including infection, would confound the diagnosis or evaluation of stania dermatitic diagnosis and evaluation. 		
	 Use of other investigational drugs within 5 half-lives of enrollment, or within 30 days /until the expected pharmacodynamic effect has returned to baseline, whichever is longer. History of hypersensitivity to any of the study drug constituents or to drugs of similar chemical classes. 		
Key Exclusion	 Risk factors for Torsades de Pointes including uncorrected hypokalemia or hypomagnesemia, history of cardiac failure, or history of clinically significant/symptomatic bradycardia or any of the following: Long QT syndrome, family history of idiopathic sudden death or congenital long QT syndrome 		
Citteria	 Concomitant medication(s) with a "Known Risk of Torsades de Pointes" that cannot be discontinued or replaced by safe alternative medication. 		
	 Resting QTcF ≥450 msec (male) or ≥470 msec (female) at screening or baseline or inability to determine the QTcF interval 		
	Cardiac or cardiac repolarization abnormality		
	 Subjects with pre-existing conditions that may confound ability to diagnose drug-induced liver injury (DILI) or subjects with factors that increase susceptibility to DILI 		
	Participation in prior ZPL389 studies		
Study treatment	 ZPL389 in one of 4 dosing levels or placebo will be administered orally in capsules in the following dosing groups: Placebo once daily ZPL389 dose 1 once daily ZPL389 dose 2 once daily ZPL389 dose 3 once daily ZPL389 dose 4 once daily 		
Efficacy	Investigator's global assessment; Eczema Area and Severity Index		
Key safety assessments	Adverse event monitoring, physical examinations including vital signs, monitoring of laboratory markers in blood and urine and electrocardiograms		
Other assessments			
Data analysis	The Multiple Comparison Procedures-Modelling methodology will be used to determine an overall dose-response signal with respect to Investigator's global assessment response at Week 16. Summary statistics for continuous variables will include N, mean, standard deviation, minimum, lower quartile, median, upper quartile, maximum. Summary statistics for discrete variables will be presented in contingency tables and will include absolute and relative frequencies. If not otherwise specified, p-values will be presented as two-sided p-values and two-sided confidence intervals will be displayed.		
Key words	atopic dermatitis, AD, eczema, atopic eczema, itch, pruritus, histamine 4 receptor antagonist, H4R, ZPL389		

1 Introduction

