4.1 Inclusion criteria

Subjects eligible for inclusion in this study must fulfill **all** of the following criteria:

- 1. Written informed consent must be obtained before any assessment is performed.
- 2. Females and males aged 18 years or older at the time of Screening
- 3. Chronic AD; according to American Academy of Dermatology Consensus Criteria (Eichenfield et al 2014), that has been present for at least 1 year before the baseline visit.
- 4. Moderate to severe AD defined as:
 - Eczema Area and Severity Index (EASI) ≥16 at Screening and at Baseline
 - IGA 3 or 4 on a 5-point scale (where 3 is moderate and 4 is severe) at Screening and Baseline
 - BSA involvement $\geq 10\%$ at Screening and Baseline
- 5. Average peak pruritus score \geq 3 as assessed by NRS over the last 7 days prior to Baseline
- 6. Documented recent history (within 6 months before the screening visit) of inadequate response to treatment with topical medications for AD or for whom topical treatments are otherwise medically inadvisable (e.g., because of important side effects or safety risks).
- 7. Candidate for systemic treatment
- 8. Have applied a stable dose of bland topical emollient once daily for at least the 7 consecutive days immediately before the baseline visit
- 9. Willing and able to comply with scheduled visits, treatment plan, laboratory tests, diary completion and other study procedures.

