9.4.2 Statistical model, hypothesis, and method of analysis

The null hypothesis of a constant dose-response curve for the primary efficacy endpoint will be tested at a significance level of 5% against the one-sided alternative hypothesis of a nonconstant dose response curve using the MCP-Mod methodology.

A logistic regression model will be fitted with response as outcome variable and treatment (dose as categorical variable) and baseline IGA as covariates.

The response Y_{ij} for subject *j* in dose group *i* receiving dose d_i is modelled as $Y_{ij} \sim Bin(1, p_{ij})$ with $p_{ij} = logit^{-1}(\delta_i + \mathbf{x}_{ij}; \boldsymbol{\beta}), i=1,...,5, j=1,..., n_i$

where Bin(1,*p*) denotes the binomial distribution with parameter 1 and *p*, δ_i is the effect of dose d_i , β refers to the vector of regression coefficients corresponding to additional covariates x_{ij} which represent the baseline IGA category. Finally, n_i is the number of subjects allocated to each treatment group. If the covariate baseline IGA prevents fitting of a model, it will be dropped.

Population-average estimates of the logit of the response probability for each dose will be derived based on the results of the logistic regression. This will be a weighted sum of the corresponding estimates for each baseline IGA. The weights will be based on the observed frequencies of the baseline IGA category in the FAS.

The covariance matrix of the estimates will also be estimated based on the logistic regression results. Using the obtained estimates and estimated covariance matrix generalized MCP-Mod (Pinheiro 2014) will be performed.

The following dose-response shapes are selected as candidates:

- 1. Sigmoid Emax model (with fixed Hill parameter): $f(d, \theta) = E0 + Emax^*dh/(dh + ED50h)$
- sigEmax1: ED50 = 25 mg, Hill parameter = 4.0
- sigEmax2: ED50 = 30 mg, Hill parameter = 8.0
- sigEmax3: ED50 = 1.85 mg, Hill parameter = 3.0
- sigEmax4: ED50 = 7.5 mg, Hill parameter = 5.0
- 2. Emax model: $f(d, \theta) = E0 + Emax*d/(d+ED50)$
- Emax1: ED50 = 15 mg
- Emax2: ED50 = 45 mg
- 3. beta model: E0+Emax*B($\delta 1$, $\delta 2$)*x^{$\delta 1$}(1-x)^{$\delta 2$} with x=d/scale
- Scale=71, δ1=1.1, δ2=1.1

Figure 9-1Candidate models for IGA response at Week 16

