9.8 Sample size calculation

The primary objective of this study is to characterize the dose response relationship among ZPL389 doses (3, 10, 30 and 50 mg o.d.) and placebo with respect to achievement of IGA response after 16 weeks of treatment. The sample size was determined with the software ADDPLAN DF, version 3.1.8, with settings for minimum power function and model based contrasts.

The sample size is derived to detect a dose-response with 90% power and a one-sided alpha of 2.5%. Based on literature data Simpson et al 2017, a placebo response rate of 10% is assumed. A maximum treatment effect for ZPL389 of 20%-points higher than placebo is assumed. An

unbalanced allocation ratio of 2:1:1:2:2 corresponding to treatment arms placebo: 3 mg: 10 mg: 30 mg: 50 mg, with more subjects allocated to placebo and the higher doses, is chosen to increase the precision of the estimate for the treatment effect at doses in the expected efficacious dose range.

Under these assumptions, a sample size of 360 subjects in total will be required, randomized to 90:45:45:90:90 subjects corresponding to placebo: 3 mg: 10 mg: 30 mg: 50 mg treatment arms.

In order to show consistency of the treatment effect in Japanese subjects compared to the non-Japanese population, it was estimated that approximately 40 Japanese subjects need to be recruited, i.e. the trial will include approximately 320 non-Japanese subjects and 40 Japanese subjects and the total sample size is 360 subjects.

10 Ethical considerations

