# 2.5.2 Statistical hypothesis, model, and method of analysis

The key questions to address this objective are

- Is there a dose-response relationship for IGA response after 16 weeks of treatment?
- What is the form of this dose-response?

• What doses deliver sufficient efficacy in terms of IGA response after 16 weeks of treatment?

Results from the interim analysis indicate that there is no dose-response relationship and therefore the second and third questions are no longer relevant. Thus the analysis of the primary variable will focus only on the logistic regression analysis described in the protocol, establishing the presence or absence of a dose-response relationship. The MCP-Mod procedure as outlined in the protocol will not be carried out.

The primary objective will be achieved if the null hypothesis of no difference between treatment groups is rejected at 5% one-sided level.

A logistic regression model will be fitted with IGA response as the outcome variable and treatment (dose as categorical variable) and baseline IGA as covariates.

The response  $Y_{ij}$  for subject j in dose group i receiving dose  $d_i$  is modelled as  $Y_{ij} \sim Bin(1, p_{ij})$  with  $p_{ij} = logit^{-1}(\delta_i + \mathbf{x}_{ij}; \boldsymbol{\beta}), i=1,..., 5, j=1,..., n_i$ 

where Bin(1,p) denotes the binomial distribution with parameter 1 and p,  $\delta_i$  is the effect of dose  $d_i$ ,  $\beta$  refers to the vector of regression coefficients corresponding to additional covariates  $x_{ij}$  which represent the baseline IGA category. Finally,  $n_i$  is the number of subjects allocated to each treatment group. If the covariate baseline IGA prevents fitting of a model, it will be dropped.

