## 5.2.3 Multiple imputations for response variables

Where multiple imputation is specified, the missing data will be imputed based on the individual treatment arm information.

Multiple imputation (MI) is a simulation based approach where missing values are replaced by multiple Bayesian draws from the conditional distribution of missing data given the observed data and covariates, creating multiple completed data sets.

Missing values will be imputed simultaneously based on an underlying joint normal distribution and using a Markov Chain Monte Carlo (MCMC) method.

The imputations will be done separately for each treatment group including baseline IGA, geographical region, baseline EASI score as additional covariates.

The number of imputations will be set to 100, the seed for the random function will be set to 3892203 for this study. To generate the multiple imputed data sets, the SAS procedure MI can be used as follows:

The input data set should have one record per subject with baseline EASI score and IGA score as well as the variables to be imputed (e.g. changes from baseline in EASI, or post-baseline IGA score).

Programming notes:

- The SAS procedure MIANALYZE expects a variable called "\_IMPUTATION\_" which is generated by the MI procedure. It might be needed to set the SAS option "VALIDVARNAME=UPCASE" temporarily in the program before the MI call, this option should be reset after the MIANALYZE call to VALIDVARNAME=V6.
- In case there are no missings in one treatment group, the MI procedure does not impute any values. In this case the corresponding data need to be imputed manually outside PROC MI and added to the dataset <impdata>.

The imputed data are saved in data set <impdata>. The outcomes of interest, i.e. the EASI 50/75 response and IGA 0 or 1 response will be calculated, e.g. as follows:

The treatment differences for each imputed data set will then be evaluated by Logistic regression and ODDS ratio as described in Section 5.4.2.2. This analysis will be done by \_IMPUTATION\_ for the comparison to the placebo treatment group. The model should be estimating response probability = 1 by using DESECENDING option. Using the ESTIMATE

option in the GENMOD procedure and the ODS OUTPUT data set "Estimates" provides the estimate for the odds ratio and confidence intervals.

```
PROC GENMOD <option>;
CLASS <stratum> <treatment>;
MODEL <response> = <explanatory variables> / link=logit dist=bin type3;
BY <by-variables);

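### The logistic model for Week 16 IGA response leaves out baseline EASI, a small and avoidable loss of efficiency if EASI predicts response beyond IGA category

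*Protocol*

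**What the plan says.** The data analysis entry of the Protocol summary says that MCP-Mod will be used to "determine an overall dose-response signal with respect to Investigator's global assessment response at Week 16"; the covariates are given in the sections that follow. Protocol 9.4.2 and SAP 2.5.2 both model IGA response with "treatment (dose as categorical variable) and baseline IGA as covariates". SAP 5.2.2 describes the logistic model with geographical region added if possible, and its sample code shows weight and stratum terms. The logistic regression for responses by visit in Protocol 9.5.1 has treatment, baseline IGA and region. None of these contains baseline EASI.

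EASI is available and is used elsewhere:

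- Protocol 4.1 requires "Eczema Area and Severity Index (EASI) ≥16 at Screening and at Baseline", so every eligible patient has a value.
- SAP 5.2.3 runs the imputation by treatment group, "including baseline IGA, geographical region, baseline EASI score as additional covariates".
- The EASI model in Protocol 9.5.1 and SAP 2.6.7 includes baseline EASI together with baseline IGA, plus a baseline-by-visit interaction.

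Protocol 5.1 explains the choice of IGA: response was related to it in the proof-of-concept study, so it became a stratification factor. SAP 2.5.2 and section 4 drop MCP-Mod. The primary objective then rests on rejecting equality of the treatment groups in the logistic regression. SAP 2.5.1 names the difference in response rates as the summary measure.

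**The concern.** With MCP-Mod gone, the covariates in the logistic model directly affect the trial's main test. Baseline IGA takes only two values here, 3 or 4. By Protocol Appendix 5 it is mainly morphological: extent settles indeterminate cases and is named only for the severe grade, and excoriations are not counted. EASI (Protocol 6.4.3) grades area in four body regions and includes excoriation. Patients within one IGA category can therefore differ in the severity that EASI measures.

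If that difference predicts response, two things follow. The treatment test has less power than the collected data allow. And in the realised sample, the estimate for each dose moves with whatever EASI imbalance chance has produced. Both matter somewhat more in a trial stopped early, with fewer patients than planned and a main finding that may be negative.

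**Working it through.** **Planned power.** Protocol 9.8 states: "The sample size is derived to detect a dose-response with 90% power and a one-sided alpha of 2.5" per cent. It adds that "a placebo response rate of 10% is assumed" and "A maximum treatment effect for ZPL389 of 20%-points higher than placebo is assumed", with arms of 90:45:45:90:90. Using optimal contrasts for the seven candidate shapes, a multivariate-normal critical value of 2.31 and the minimum power over shapes:

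- logit scale with model variances: 91.7% to 91.9%;
- probability scale with common variance 0.3 × 0.7: 89.3%.

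Both agree with the stated 90%. Other variance choices give about 84% to 98%. The analysis itself is "tested at a significance level of 5% against the one-sided alternative hypothesis", a different level from the one used for sizing. Each comparison below uses one level for both models, so this mismatch does not affect the with/without contrast.

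**Assumptions for the comparison (not in the documents).** 40% severe at baseline; severe versus moderate odds ratio 0.5; EASI normal within IGA category; odds ratio per SD of EASI, given IGA, of 0.8, 0.67 or 0.5; no missing data. N = 187 is the interim number (SAP 1.1), used because the final number is not stated. Split 2:1:1:2:2 it gives 47:23:23:47:47. The 4-df Wald test follows the Type III Wald tests in SAP 5.2.2, taken at 5%. The trend test is the protocol's MCP-Mod test at one-sided 2.5%.

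Power in %, without → with EASI:

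| Test, N, response rates | 0.8 | 0.67 | 0.5 |
|---|---|---|---|
| Wald, 187, 10 to 30% | 47 → 47 | 49 → 50 | 46 → 52 |
| Wald, 187, 10 to 25% | 23.5 → 24.1 | 22.5 → 23.9 | 21.9 → 25.2 |
| Wald, 360, 10 to 25% | 63.5 → 64.1 | 63.0 → 64.8 | 64.0 → 68.5 |
| Trend, 187, 10 to 25% | 45.5 → 45.7 | 45.9 → 47.1 | 46.9 → 49.1 |
| Trend, 360, 10 to 25% | 83.2 → 83.7 | 84.1 → 84.8 | 84.5 → 87.2 |
| Trend, 360, 10 to 30% (three shapes) | 95.5–97.0 → 95.4–97.1 | 95.8–97.0 → 96.0–97.1 | 96.1–97.0 → 96.4–98.0 |

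The 25% rows match the 15-point target effect in Protocol 9.4.2. They use 4,000 trials each, so the simulation error of a single power is at most √(0.25/4000) = 0.8 points; the gains are paired on the same data and are tighter. The gain is 0 to 6 points at 187. At 360 it is 0 to 3 points for the trend test, and up to 4.5 in one Wald setting.

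A likelihood-ratio version (45% severe, odds ratio per SD 0.5 to 0.75) gives gains of 0.5 to 3.6 points at 187 and 0.1 to 1.7 at 360. That test is oversized in arms this small: its null rejection at 187 is 6.8% to 7.8%. Its gains are therefore supporting evidence only.

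**Type I error.** Null rejection of the trend test is 1.5–1.9% without EASI and 1.5–2.1% with it. For the likelihood-ratio test at 187 it is 6.8% against 7.1% (odds ratio per SD 0.5). The Wald runs show no inflation, and no loss of power beyond noise when EASI is not prognostic.

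**Where the gain comes from.** At odds ratio per SD 0.5 and N = 360, under one Emax shape, the 50 mg log odds ratio goes from 1.403 (SE 0.429) to 1.515 (SE 0.447). The ratio to its SE rises from 3.27 to 3.39, which is (3.39/3.27)² ≈ 1.07, or about 7% more information. The SE increases, but the conditional estimate increases more.

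**Chance imbalance.** The 95% limit for the difference in mean EASI, in SDs, is 1.96 × √(1/n₁ + 1/n₂). For 23 versus 47 this is 1.96 × 0.254 = 0.50; for 45 versus 90 it is 1.96 × 0.183 = 0.36. The odds ratio then shifts by a factor of (odds ratio per SD)^(−limit):

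- 23 versus 47: 0.8^(−0.50) = 1.12 to 0.5^(−0.50) = 1.41;
- 45 versus 90: 1.08 to 1.28.

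For comparison, at 10% response in both arms the SE of the log odds ratio for 23 versus 47 is √(1/(23 × 0.09) + 1/(47 × 0.09)) = 0.85. Its 95% interval multiplies or divides the odds ratio by exp(1.96 × 0.85) ≈ 5.3. In simulation at 360, the 3 mg log odds ratio moves by about 0.2, 0.4 or 0.7 per SD of imbalance (odds ratio per SD 0.8, 0.67, 0.5) without EASI, and by about zero with it.

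**The case against.** The covariate in the plan has a documented reason (Protocol 5.1); EASI has none. In the repeated-measures model EASI is the baseline of the outcome itself, and in the imputation it is an auxiliary variable. Neither use shows that it predicts IGA response beyond IGA. This stands: the gain is conditional on a strength that has to be assumed, and it is under 2 points in every row above at 0.67 or weaker.

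Sparse data are a fair worry. A 23-patient arm at 10% response has about 2 responders, and SAP 5.2.2 already warns of non-convergence. A rule applied dataset by dataset could also leave different models across the 100 imputations. This does not remove the gain, but it does require one rule for all imputations.

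The SAP is dated September 2020, after the May 2020 interim, so a new covariate in the primary model is a change made with results known. That also stands, and is why the protocol's model should be shown beside it. Finally, the summary measure is a rate difference that SAP 2.6.7 computes from simple rates, so adding EASI to the logistic model alone would not change it.

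A reader might go further and infer that the dose estimates are biased, or that a finding of no dose-response is unsafe because severity was not adjusted for. The documents do not support this. Allocation is randomised and stratified by IGA, which already balances part of severity. Chance imbalance is not bias, and the standard error covers it. Nor is it accurate to say that the plan adjusts for baseline IGA alone: SAP 5.2.2 also brings in region.

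**Conclusion.** The omission is real in every version of the response model, and its consequence is small. For an odds ratio per SD of 0.5 to 0.8, adding EASI is worth about 0 to 6 points of power at an assumed 187 patients and about 0 to 3 points at 360. The upper ends need the strongest assumed relation. If EASI carries no information beyond IGA, nothing is gained and nothing material is lost. Within the realised trial, adjustment also makes the dose estimates insensitive to EASI imbalance, although a shift of 1.12 to 1.41 at the 95% limit is well inside a confidence interval about 5.3-fold wide on either side.

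This is an efficiency improvement at very low cost. It does not show an error in the plan, an inflated false-positive rate or a reason to doubt a negative result. The figures rest on the assumed prognostic strength, share of severe patients and sample size, and on complete data; the multiple-imputation step was not simulated.

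**What to change.** Before database lock:

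1. Add baseline EASI as a linear covariate to the logistic model in SAP 2.5.2 and 5.2.2 for IGA, EASI50 and EASI75 response.
2. State that EASI is the first term dropped if the model fails to converge in any imputed dataset, and that the same model is then used in all 100 imputations. The existing order in 5.2.2 follows after that.
3. Report covariate-standardised differences in response rates, each dose against placebo, so that the adjusted analysis delivers the summary measure in SAP 2.5.1.
4. Reconcile SAP 2.5.2 with 5.2.2 on region, and correct the sample code to the model chosen.
5. Report the protocol's model (dose and baseline IGA) alongside, because the SAP follows the interim analysis.

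The cost is one model term, a few lines of text and a standardisation step. There are two downsides. One more parameter is estimated from few responders: at 187 patients, about 19 if every arm is at 10% (187 × 0.10). Under the Emax shape with ED50 15 mg rising to 30% the count is about 40 (47 × 0.100 + 23 × 0.143 + 23 × 0.204 + 47 × 0.273 + 47 × 0.300). And the odds ratio becomes conditional on EASI as well as IGA, so it is not directly comparable with the unadjusted one; the standardised rate difference avoids that problem.
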